A patient will be considered a responder in Part A if he or she did not receive a blood transfusion from Week 5 through Week 26 (EOT) and did not receive treatment for CAgD beyond what is permitted per protocol. Additionally, the patient's Hgb level must meet either of the following criteria:

- Hgb level is ≥ 12 g/dL at the treatment assessment endpoint (defined as mean value from Weeks 23, 25, and 26), *or*
- Hgb increased ≥ 2 g/dL from baseline (defined as the last Hgb value before administration of the first dose of study drug) at treatment assessment endpoint

Note: Any patient withdrawing from the study after Week 5 and prior to the Week 23 visit will be considered a non-responder.

A list of excluded concomitant medications, as well as allowed concomitant medications with restrictions, is provided in [Section 6.2.6](#). Beyond the permitted concomitant medications, study drug, and transfusions, patients may receive no other therapies for the treatment of CAgD while enrolled in this study; patients requiring other treatment for their CAgD in Part A will be withdrawn from the study and counted as non-responders. These patients will not be eligible to participate in Part B.

Part B

Following completion of dosing in the 6-month treatment period, patients will continue to receive BIVV009 dosing during Part B, the long-term safety and durability of response extension phase. Part B will run for 2 years following last patient out (LPO) under Part A. Patients requiring treatment with permitted concomitant medications and/or transfusions will not be discontinued from the study. Patients in Part B will be transfused per the Transfusion Criteria in [Table 1](#). Patients who receive a transfusion during Part B will not be withdrawn from the study.

Patients will be dosed with BIVV009 every 2 weeks, as in Part A. Should patients deviate from their scheduled dosing, a repeat loading dose may be required. On-site visits will be completed ~ every 3 months (at a minimum) for collection of PK, PD and ADA samples during the 1st year of treatment in Part B, then every 6 months and for additional safety and efficacy measures.

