6.2.6 Concomitant medications

Patients will refrain from participation in any other investigational study drug trial in which receipt of any investigational drug occurred within 5 half-lives or 30 days, whichever is longer, prior to Day 0 and during the entire study.

Treatment with rituximab monotherapy or rituximab combination therapies (eg, with bendamustine, fludarabine, ibrutinib, or cytotoxic drugs) is prohibited.

During Part A, patients will not take any prescription or over-the-counter medications/products until completion of the follow-up assessments, unless prescribed by the Investigator or another physician for the treatment of an AE.

As noted in [Section 5.2](#), concurrent administration of erythropoietin and/or a daily dose of corticosteroids (equivalent to ≤ 10 mg/day of prednisone) is acceptable provided the patient has been on a stable dose during the previous 3 months; concurrent use of vitamin B12, folate and iron supplementation is acceptable provided the patient has been on a stable dose during the previous 4 weeks.

Topical therapies without risk of systemic absorption may be allowed, and non-prescription medications for treatment of minor intercurrent illnesses (headache, viral upper respiratory tract infections, etc.) are permitted at the discretion of the PI. Hormonal contraception in female patients is allowed provided patients are receiving stable treatment ≥ 3 months prior to Screening. Any medication taken by the patient during the study, along with its strength, frequency of dosing, and reason for its use, will be documented in the patient's source data and the eCRF.

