2.2. Study Endpoints

2.2.1. Primary Endpoint

The primary efficacy endpoint is the responder rate defined as follows (Table 2 of protocol):

A patient will be considered a responder if he or she did not receive a blood transfusion from Week 5 through Week 26 (end of treatment [EOT]) and did not receive treatment for CAD beyond what is permitted per protocol. Additionally, the patient's Hgb level must meet either of the following criteria:

- Hgb level is ≥ 12 g/dL at treatment assessment endpoint (defined as mean value from Weeks 23, 25, and 26), or
- Hgb increased ≥ 2 g/dL from baseline (defined as the last Hgb value before administration of the first dose of study drug) at treatment assessment endpoint

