Medical review of medical history and AEs will ascertain thromboembolic events for analysis.

Normalization of Bilirubin

The normalization of bilirubin is defined as total bilirubin \leq upper limit of normal (ULN) (specified by the central lab).

Normalization of LDH

The normalization of LDH is defined as LDH value \leq ULN (specified by the central lab).

Normalization of Haptoglobin

The normalization of haptoglobin is defined as haptoglobin above the level of detection.

Hemolytic Breakthrough

Hemolytic breakthrough at any visit is defined as

- A decrease of 2 g/dL or more in Hgb from the last scheduled visit, and
- One of the followings:
 - An increase in LDH from the last scheduled visit,
 - An increase in bilirubin from the last scheduled visit, or
 - A decrease in haptoglobin from the last scheduled visit.

Protocol Prohibited CAD Medications

The following concomitant medications are prohibited during the study treatment period in Part A:

- Rituximab alone or as part of combination therapy
- Cytotoxic drugs (such as fludarabine, bendamustine, ibrutinib, cyclophosphamide)
- Other investigational drug

The efficacy endpoint (estimand) accounting for protocol prohibited CAD medication use will be based on the eCRF questionnaire “Did the subject receive any prohibited medications since the last visit?” at post-baseline visits. The medical review for the list of prohibited medications will be reconciled with the eCRF questionnaire.

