6.4. Non-study Drug Medications

6.4.1. Concomitant Medications

Prior medications are those taken before the first dose of study drug. Concomitant medications are those administered on or after the first dose of study drug, or those administered before the first dose that are ongoing when study treatment begins. Prior and concomitant medications will be coded using World Health Organization drug enhanced dictionary (March 2017 version or higher) and summarized using the FAS.

Separate tables will be generated to summarize prior CAD medical treatment, concomitant CAD medical treatment, and protocol prohibited CAD treatment.

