7.2. Primary Endpoint

The primary endpoint, defined in [Section 2.2.1](#), is a composite endpoint of the following components:

1. Free of post-baseline transfusion within the range of Week 5 and Week 26 visit dates;
2. Hgb at treatment assessment timepoint ≥ 12 g/dL, or the change from baseline at treatment assessment ≥ 2 g/dL,
3. Receive no protocol prohibited medications defined in [Section 5.1.1](#).

Components 1 and 3 will be determined by the corresponding questions in eCRF at all visits (from Week 5 through Week 26) in Part A.

To be evaluable for each of the components, a subject must be observed through at least Week 23 visit. Discontinuation of study treatment prior to Week 23 visit will result in an unknown status for Components 1 and 3. Missing Hgb value at all visits of Week 23, 25, and 26 will result in an unknown status for Component 2.

In the event of unknown status in any of the components, a subject may be a responder, non-responder, or missing for the response status. A subject is considered responder, if the subject meets all of the three components; a subject is considered a non-responder, if the subject is known to not meet any of the three components; otherwise, a subject is considered missing in response status.

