7.2.2. Sensitivity Analyses

Sensitivity analyses will be carried out based on the completer estimand and the per-protocol estimand (defined in [Table 3](#)). The proportion of subjects with treatment response will be summarized along with the 95% exact Clopper-Pearson CI.

Table 3: Estimands for Primary Endpoint

	Composite Estimand	Completer Estimand	Per-protocol Estimand
Population	FAS	A subset of FAS with those who complete treatment at least through Week 23 and have at least 1 evaluable Hgb from Week 23, 25, and 26	A subset of FAS with those who are free of important protocol deviations defined in Section 6.3
Response Variable	Responder if 
 Free of post-baseline transfusion within the range of Week 5 and Week 26 visit dates, and Hgb at treatment assessment timepoint ≥ 12 g/dL, or the change from baseline at treatment assessment ≥ 2 g/dL, and Receive no protocol prohibited medications defined in Section 5.1.1 within the range of Week 5 and Week 26 visit dates, and Remain in study through at least Week 23, and At least 1 evaluable Hgb from Weeks 23, 25, and 26 	Responder if 
 Free of post-baseline transfusion within the range of Week 5 and Week 26 visit dates, and Hgb at treatment assessment timepoint ≥ 12 g/dL, or the change from baseline at treatment assessment ≥ 2 g/dL, and Receive no protocol prohibited medications defined in Section 5.1.1 within the range of Week 5 and Week 26 visit dates 	Responder if 
 Free of post-baseline transfusion within the range of Week 5 and Week 26 visit dates, and Hgb at treatment assessment timepoint ≥ 12 g/dL, or the change from baseline at treatment assessment ≥ 2 g/dL
Treatment effect	Proportion of subjects who achieve the composite response variable (defined above)	Proportion of subjects who achieve the treatment response	Proportion of subjects who achieve the treatment response

In the case when there are at least 2 subjects who discontinue study participation prior to Week 5, a supportive analysis, similar to the primary analysis, will be performed by excluding those subjects who discontinue prior to Week 5.

In the case of normal ranges (LLN) varying across local labs, a sensitivity analysis will be performed for the primary endpoint by qualifying normalization of Hgb using \geq LLN, instead of ≥ 12 g/dL.

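### SAP Table 3 scores the no-other-treatment component of the primary endpoint against a three-entry drug list and only from Week 5, which is narrower than the responder definition in protocol Table 2 and SAP 2.2.1

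*SAP*

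**What the plan says.** **The stated definition.** Protocol section 4.1, Table 2, requires that a responder "did not receive treatment for CAgD beyond what is permitted per protocol". Part A SAP section 2.2.1 has the same criterion: "did not receive treatment for CAD beyond what is permitted per protocol". In both, the Week 5 to Week 26 window belongs to the separate transfusion clause. The protocol text after Table 2 adds that "patients requiring other treatment for their CAgD in Part A will be withdrawn from the study and counted as non-responders". That sentence covers Part A without a Week 5 start.

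**The scored definition.** SAP section 7.2 says the endpoint is the one defined in 2.2.1. It then replaces the treatment clause with a third component, no prohibited medication as listed in section 5.1.1. On the data source it says: "Components 1 and 3 will be determined by the corresponding questions in eCRF at all visits (from Week 5 through Week 26" in Part A). Table 3 in section 7.2.2 requires, for the composite and completer estimands, "Receive no protocol prohibited medications defined in Section 5.1.1 within the range of Week 5 and Week 26 visit dates".

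**The list.** Section 5.1.1 names rituximab alone or in combination, cytotoxic drugs, and other investigational drugs, all barred throughout Part A treatment. It bases the estimand on the eCRF question about prohibited medication "at post-baseline visits. The medical review for the list of prohibited medications will be reconciled with the eCRF questionnaire".

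**What the protocol permits.** Section 6.2.6 states: "During Part A, patients will not take any prescription or over-the-counter medications/products until completion of the follow-up assessments", with an exception for drugs prescribed to treat an adverse event. It accepts erythropoietin and low-dose corticosteroid only at a dose stable for 3 months.

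**The concern.** The rule that decides the trial's one formal hypothesis differs from the definition it claims to implement, in two ways: which treatments count, and from when. Protocol section 7 lets the SAP prevail over the protocol. That does not settle SAP 2.2.1 against SAP 7.2 and Table 3.

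The SAP also gives component 3 more than one start point. Section 5.1.1 uses all post-baseline visits, section 7.2 uses visits from Week 5, and Table 3 uses dates from the Week 5 visit.

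The main risk is an inflated response rate. SAP section 5.1.4 itself expects rituximab or combination use to follow mostly from lack of response or breakthrough, so patients who need added CAD treatment are those the clause is meant to fail. The error could also run the other way: the list entries carry no indication limit, so a listed drug given after Week 5 for a non-CAD reason could be failed under Table 3 though not under Table 2.

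**Working it through.** **1. The plan's own figures.** Inputs from protocol section 7.10 and SAP 3.3: N = 20, null rate 30%, assumed rate 66%, exact 95% Clopper-Pearson lower limit above 30%, minimum success 11/20.

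- Lower limit = Beta quantile(0.025; x, n − x + 1). For 11/20 this is 31.5%; for 10/20 it is 27.2%. So 11 is the minimum, as stated.
- Power = P(X ≥ 11 | 20, 0.66) = 0.897, against 90% stated.
- Attained one-sided type I error = P(X ≥ 11 | 20, 0.30) = 0.017.

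The design reproduces. The issue is what counts as a response.

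**2. The two rules side by side.**

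| | Protocol Table 2 / SAP 2.2.1 | SAP 7.2 / Table 3 |
|---|---|---|
| Scope | Any CAD treatment beyond what is permitted | Three-entry list in SAP 5.1.1 |
| Start | None given; the protocol text after Table 2 covers Part A | Week 5 |

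**3. How much time goes unscored.** The post-baseline Part A visits are Day 7, then Day 21 to Day 175 every 14 days, then Day 182: 1 + 12 + 1 = 14. Two of them (Days 7 and 21) precede Week 5 (Day 35), which leaves 12.

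- Under section 7.2, the first scored eCRF answer looks back to the previous visit, so the unscored period is Day 0 to 21: 21/182 = 11.5%.
- Under Table 3, scoring starts at the Week 5 visit date, so it is Day 0 to 35: 35/182 = 19.2%.

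**4. Routes by which a patient the definition fails is scored a responder** (Hgb and transfusion criteria being met).

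- (a) Off-list CAD treatment without withdrawal before Week 23. Examples are erythropoietin newly started for CAD, which is not the stable dosing that protocol 6.2.6 accepts, or a non-drug CAD therapy, a category SAP 6.4.2 summarizes and lists.
- (b) A listed drug before Week 5 without withdrawal before Week 23.
- (c) Off-list CAD treatment after the Week 23 visit, Day 161 to 182 (21 days, 21/182 = 11.5%). Even if the patient is then withdrawn, the composite estimand's Week 23 rule is already satisfied, and Table 3 does not carry over the protocol's non-responder statement.

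**5. Effect of one such patient.** 1/20 = 5 percentage points. The result flips only if the scored count is exactly 11. With the scored count Binomial(20, p), P(X = 11) is:

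| p | 30% | 40% | 50% | 55% | 66% |
|---|---|---|---|---|---|
| P(X = 11) | 1.2% | 7.1% | 16.0% | 17.7% | 10.6% |

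These are upper limits on how often one such patient could decide the trial, before allowing for the chance that such a patient exists.

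**6. Would the planned sensitivity analyses show it?** Take 11/20 with one misclassified responder and no dropouts or other exclusions.

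- Listed drug before Week 5: the per-protocol set removes the patient, because SAP 6.3 covers the whole Part A treatment period. It gives 10/19, lower limit 28.9%, so the problem is visible.
- Off-list treatment: the composite, completer and per-protocol analyses all give 11/20, lower limit 31.5%. Only the treatment tables would reveal it.

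**The case against.** The strongest reply is that this is a difference of wording with little practical reach.

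- **The list covers the main drugs.** Protocol 6.2.6, to which the text after Table 2 refers, names rituximab regimens and other investigational drugs as excluded, and SAP 5.1.1 covers these and adds cytotoxics generally. This stands. What remains off-list is mainly a new start or dose change of a conditionally permitted drug, plus non-drug therapy. Some new starts might be allowed as treatment of an adverse event.
- **The Week 5 window was intended.** SAP section 10 records it as a clarification. That shows intent, but 2.2.1 was left as it was, and intent about the window does not explain the narrower treatment scope.
- **The eCRF question names no list**, so a site could answer yes for an off-list treatment. However, the answer is reconciled with a medical review of prohibited medications, and 7.2 and Table 3 both point to 5.1.1.
- **Such patients are withdrawn.** The protocol text after Table 2 says so, and Part B SAP 3.1.1 reads it that way. But protocol 5.3 says only that patients may be withdrawn, and withdrawal gives non-response only before Week 23.
- **A closed list is reproducible, and medical review in an open-label trial adds judgement.** This is a fair cost, and a reason to write the review rule in advance.
- **The section 5.1.1 heading refers to CAD medications**, which weakens the point that a listed drug for another indication would be failed. The entries themselves state no indication, so the case is unsettled.

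**Conclusion.** The concern holds. Followed as written, Table 3 can count as a responder a patient whom protocol Table 2 and SAP 2.2.1 define as a non-responder, and the SAP's own start points for component 3 disagree. SAP 6.4.1 shows that the broader category is recognised: "Separate tables will be generated to summarize prior CAD medical treatment, concomitant CAD medical treatment, and protocol prohibited CAD treatment". Only the last of these is scored.

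The gap is narrow. It needs CAD treatment outside the list, or a listed drug before Week 5, in a patient who is not withdrawn before Week 23, or off-list treatment in the last 21 days. The documents give no frequency, so the size is illustrative: 5 percentage points per patient, decisive for one patient only at exactly 11/20, which has probability 10.6% if the scored rate is 66% and at most 17.7% over the rates tabulated. The calculation assumes exactly 20 patients and a binomial count. The discrepancy should be fixed because it sits in the primary endpoint of a single-arm, open-label pivotal trial, and because off-list use would leave all three planned estimands unchanged.

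**What to change.** In SAP 5.1.1, 7.2 and Table 3, define component 3 as protocol Table 2 does: no CAD treatment beyond what the protocol permits, from first dose through Week 26. Determine it by medical review, under a written rule, of the concomitant-medication and other-therapy data together with the eCRF question at all post-baseline visits. State one start day, and state how a listed drug given for a non-CAD reason is scored. The protocol passages on withdrawal for other CAD treatment (4.1 and 5.3) should be reconciled. At minimum, add the Table 2 rule as a pre-specified sensitivity analysis of the primary endpoint.

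The cost is SAP wording before the Part A lock and a little adjudication. Drug, strength, frequency and reason are already recorded under protocol 6.2.6, and the treatment summaries are already planned in SAP 6.4.1, 6.4.2 and 12. N, the significance level and the 11/20 threshold do not change; the reported rate may move slightly in either direction. If the Part A data are already locked (protocol 4.3.8 and the Part B SAP introduction describe parts of Part A in the past tense), the same rule can be run as a supplementary analysis, labelled as such.

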7.2.3. Subgroup Analyses

The proportion of subjects with response according to the composite estimand will be summarized for subgroups defined in [Section 4.6](#) along with its 95% exact CI. The consistency of the response rates among these sub-populations will be examined by forest plots.

7.3. Secondary Endpoints

7.3.1. Mean Change from Baseline in Bilirubin at the Treatment Assessment Timepoint

The change from baseline in bilirubin at the treatment assessment timepoint will be analyzed for FAS excluding subjects with Gilbert's syndrome. Gilbert's syndrome status is determined by the result of the genetic test at screening. If the result of Gilbert's syndrome test is not available for a patient, the patient will be excluded from the analysis. The primary analysis will be performed according to Hypothetical Estimand (defined in [Section 5.1.3](#)), while a sensitivity analysis will be done via De-facto Estimand ([Section 5.1.3](#)). Additional details are found in [Table 4](#).

Table 4: Estimands for Change from Baseline in Bilirubin

	Hypothetical Estimand	De-facto Estimand
Population	FAS excluding subjects with Gilbert's syndrome	FAS excluding subjects with Gilbert's syndrome
Variable	Change from baseline at treatment assessment time point, where any value after transfusion and prohibited medication is considered missing	Change from baseline at treatment assessment time point
Treatment effect	Mean change from baseline, if transfusion or prohibited medications had not been available	Mean change from baseline, irrespective of transfusion or prohibited medication use

For either estimand, the mean change from baseline in bilirubin at treatment assessment timepoint, along with its 95% CI, will be estimated by the MMRM model ([Section 5.1.4.1](#)).

If the number of subjects with unknown Gilbert's syndrome status is greater than 2, additional sensitivity analysis will be performed to include such subjects (unknown Gilbert's syndrome), whose baseline total bilirubin level is low to be considered less indicative of Gilbert's syndrome.

Additional sensitivity analysis based on multiple imputation ([Section 5.1.4.2](#)) will be carried out for the Hypothetical Estimand, utilizing the regression method with monotone missing patterns. Specifically, the following 4 imputation models will be considered:

- Change from baseline in bilirubin at treatment assessment timepoint is modeled as a function of baseline bilirubin value, weight stratum (< 75 kg, >= 75 kg), and bilirubin values from Day 7 through visits Week 21, visits prior to first transfusion, or visits prior to first prohibited medication use, whichever occurs first;
- Change from baseline in bilirubin at treatment assessment timepoint is modeled as a function of baseline bilirubin value, weight stratum (< 75 kg, >= 75 kg), and bilirubin values from Day 7 through visits Week 21, 2nd last visit prior to first transfusion, or visits prior to first prohibited medication use, whichever occurs first;
- Change from baseline in bilirubin at treatment assessment timepoint is modeled as a function of baseline bilirubin value, weight stratum (< 75 kg, >= 75 kg), and bilirubin values from Week 5 through visits Week 21 (observed value through visits prior to first transfusion, or visits prior to first prohibited medication use, whichever occurs first).
- Change from baseline in bilirubin at treatment assessment timepoint is modeled as a function of baseline bilirubin value, weight stratum (< 75 kg, >= 75 kg), and bilirubin values from Day 7 through visits Week 21 (observed value through visits prior to first transfusion, or visits prior to first prohibited medication use, whichever occurs first); but with NCMV restrictions.

7.3.2. Mean Change from Baseline in FACIT-F Score at Treatment Assessment Timepoint

The change from baseline in FACIT-F score at the treatment assessment timepoint will be analyzed for the FAS. The derivation of FACIT-F score is detailed in [Section 7.5](#). The primary analysis will be performed according to Hypothetical Estimand (defined in [Section 5.1.3](#)), while a sensitivity analysis will be done via De-facto Estimand ([Section 5.1.3](#)). Additional details are found in [Table 5](#).

Table 5: Estimands for Change from Baseline in FACIT-F Score

	Hypothetical Estimand	De-facto Estimand
Population	FAS	FAS
Variable	Change from baseline at treatment assessment time point, where any value after transfusion and prohibited medication is considered missing	Change from baseline at treatment assessment time point
Treatment effect	Mean change from baseline, if transfusion or prohibited medications had not been available	Mean change from baseline, irrespective of transfusion or prohibited medication use

For either estimand, the mean change from baseline in FACIT-F score at treatment assessment timepoint, along with its 95% CI, will be estimated by the MMRM model ([Section 5.1.4.1](#)).

Additional sensitivity analyses for hypothetical estimand, similar to those specified for bilirubin, will be performed for the change from baseline in FACIT-F score at treatment assessment timepoint.

7.3.3. Mean Change from Baseline in Lactate Dehydrogenase (LDH) at the Treatment Assessment Timepoint

The change from baseline in LDH at the treatment assessment timepoint will be analyzed for the FAS. The primary analysis will be performed according to Hypothetical Estimand (defined in [Section 5.1.3](#)), while a sensitivity analysis will be done via De-facto Estimand ([Section 5.1.3](#)). Additional details are found in [Table 6](#).

Table 6: Estimands for Change from Baseline in LDH

	Hypothetical Estimand	De-facto Estimand
Population	FAS	FAS
Variable	Change from baseline at treatment assessment time point, where any value after transfusion and prohibited medication is considered missing	Change from baseline at treatment assessment time point
Treatment effect	Mean change from baseline, if transfusion or prohibited medications had not been available	Mean change from baseline, irrespective of transfusion or prohibited medication use

For either estimand, the mean change from baseline in LDH at treatment assessment timepoint, along with its 95% CI, will be estimated by the MMRM model ([Section 5.1.4.1](#)).

Additional sensitivity analyses for hypothetical estimand, similar to those specified for bilirubin, will be performed for the change from baseline in LDH at treatment assessment timepoint.

Additional descriptive analyses will be performed for LDH isoforms.

7.3.4. Number of Transfusions and Number of Units after the First 5 Weeks of Study Drug Administration

The number of transfusions after Week 5 through Week 26 visits will be summarized for the FAS, where the observed data will be used for subjects who discontinue study treatment early in Part A. The number of units transfused during the same period of time will be summarized for subjects who receive at least 1 transfusion.

The transfusions occurring during the first 5 weeks will be listed.

